10 REGULATORY AND SAFETY REPORTING

10.1 Regulatory Compliance

The Sponsor-Investigator and Principal Investigator will conduct the protocol in adherence to the guidelines set forth by the Institutional Review Board (IRB) /Human Research Protection Office (HRPO) and the Radioactive Drug Research Committee (RDRC)/Radiation Safety Office at Washington University and the U.S. Food and Drug Administration (FDA). The Sponsor-Investigator will ensure members of the research team will comply with the adverse event reporting as described below.

The Principal Investigator, Sponsor-Investigator, Authorized User, and members of the research team will promptly review all available safety information relevant to the safety of the drug, including any findings from another source not related to this study that suggest a significant risk for human subjects. Subjects will be instructed to inform a member of the research team as soon as possible should they experience symptoms of an adverse event to begin an adverse event evaluation. AE follow-up will occur as ordered by the Principal Investigator or designee. Additional follow-up will occur until the abnormal measurements return to baseline or acceptable limits, or until monitoring is no longer warranted or stabilization as evaluated by a physician. A study team member will review the subject's medical record for clinical history and, if applicable, monitor for test results as made available.

10.2 Safety Event Definitions

For this study, the following standard definitions for reporting will be used:

10.2.1 Investigational Drug

The investigational drug named [⁶⁸Ga]Galmydar is a radioactive drug held under an Investigational New Drug (IND) application.

10.2.2 Adverse Event

Adverse Event (AE) is any untoward medical occurrence in human subjects who receive the investigational radioactive drug ⁶⁸Ga-Galmydar, whether or not considered related to the drug. An AE (also referred to as an adverse experience) may include any unfavorable and unintended sign (i.e., abnormal lab test finding), symptom, or disease temporally associated with the use of the drug, and does not imply any judgement about causality.

10.2.3 Suspected Adverse Reaction

A suspected adverse reaction is any adverse event that is determined that there is a reasonable possibility that the investigational drug caused the adverse event. For IND safety reporting, 'reasonable possibility' means there is evidence to suggest a causal relationship between the drug and the adverse event. A suspected adverse reaction implies a lesser degree of certainty about causality than an adverse reaction.

10.2.4 Adverse Reaction

Adverse Reaction means any adverse event caused by the investigational drug. Adverse reactions are a subset of all suspected adverse reactions where there is a reason to conclude that the drug caused the event.

10.2.5 Serious Adverse Event

An adverse event or suspected adverse reaction is considered serious if the event or reaction, in the view of the Principal Investigator, results in any of the following serious outcomes:

- Death,
- A life-threatening adverse event as defined as placing the participant at immediate risk of death from the AE as it occurred,
- Initial or prolonged inpatient hospitalization (hospital admission defined as ≥ 24 hours or prolongation of a hospital stay due to adverse event),
- Persistent or significant incapacity or substantial disruption of the ability to conduct normal life functions, or
- Congenital anomaly or birth defect.

10.2.6 Life-threatening

An adverse event or suspected adverse reaction is "life-threatening" if, in the view of the Principal Investigator, its occurrence places the participant at immediate risk of death. It does not include an adverse event or suspected adverse reaction that, had it occurred in a more severe form, might have caused death.

Important Medical Events (IMEs) are not immediately life-threatening, nor do they place a participant at immediate risk of death or require hospitalization. Examples of IMEs include allergic bronchospasm requiring intensive treatment in the emergency room or at home, or convulsions that do not result in inpatient hospitalization. IMEs may be serious if in the judgement of the Principal Investigator or designee they require medical or surgical intervention to prevent one of the above serious outcomes.

10.2.7 Unexpected

An adverse event or suspected adverse reaction is unexpected if is not listed at the specificity or severity that is currently

observed, or the event is not consistent with the risk information described in the protocol, informed consent form, general investigational plan or elsewhere in the current IND application. An Investigator's Brochure does not exist nor is it required for this IND. The Principal Investigator or designee will determine if an adverse event is unexpected.

Expected adverse reactions are adverse events that are known to occur for the investigational drug and should be collected in a standard, systematic format using a severity grading scale. Expectedness is assessed based on the awareness of AEs previously observed, not on the basis of what might be anticipated from the properties of the study drug. For risk related to this IND protocol, see [Expected Risks](#) section below.

10.3 Causality and Severity Assessment

The Principal Investigator or designee will make a clinical determination as to the likelihood that an AE is related to the administration of the radioactive drug or research visit procedure. Other etiologies such as pre-existing conditions, concomitant therapy, study-related procedures, accidents that occur while on study, and other external factors will be considered during the evaluation of relatedness.

Pre-existing Conditions that are present at the time of informed consent will be considered participant baseline. All baseline conditions will be recorded on the medical history in the source document forms. Worsening of the severity or frequency of a pre-existing condition in a research participant which does not necessarily have a causal relationship with the investigational drug is a reportable adverse event. Any changes, i.e., deterioration or worsening in these condition(s) shall be documented and evaluated by the Principal Investigator or designee. AEs with signs and symptoms that are believed to be due to the pre-existing condition(s) will not be reported as an AE unless there is an increase in frequency and severity.

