4.1 Study Population

We will recruit up to 38 participants for the dosimetry and rest/stress groups. Healthy adult normal volunteers (n=8, 4 males; 4 females) for whole-body imaging (dosimetry group) and patients who had a prior clinical SPECT MPI examination that is positive or negative for ischemia.

Thirty (30) subjects will be enrolled in the rest/stress group. Symptomatic patients (n=20) will have undergone a SPECT MPI examination. Ten patients in this group will have had a study positive for ischemia in two myocardial segments and referred for invasive coronary angiography (ICA) as part of their routine standard-of-care. [⁶⁸Ga]Galmydar PET imaging will occur prior to intervention. The other ten patients will have a normal SPECT MPI and no ICA referral. Subjects (n=10) who are asymptomatic and without history of cardiovascular disease will serve as a normal controls.

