6.2.1 PET Imaging Assessments and Preparation

Subjects will be instructed to fast overnight for a minimum of 6-hours prior to the scheduled appointment time. The Rest/Stress group subjects who undergo the stress PET MPI will be instructed to avoid theophylline-containing medication or dipyridamole for at least 48 hours prior to the stress imaging scan. Vasoactive medications such as calcium-channel blockers, angiotensin-converting enzyme inhibitors, β -blockers, and nitrates should be discontinued at least 24 hours before the PET perfusion examination.

The following assessments and procedures will be performed for PET imaging visits:

- Confirm eligibility. Review concomitant medications and any changes in health since the screening if assessments were performed on a separate day. Repeat between imaging days;
- Confirm or perform and document a negative urine pregnancy test for women of childbearing potential for each imaging day;
- Subjects will be requested to use the restroom to empty their bladder prior to radiotracer injection and discharge from the imaging facility;
- Place one peripheral intravenous (IV) catheter for the administration of radiotracer injection and draw blood samples for safety labs. Both the dosimetry group and the rest/stress group will have a second contralateral IV catheter placed. In the dosimetry group, one IV will be used for collection of safety labs and radiotracer metabolites and one IV will be used for the administration of [⁶⁸Ga]Galmydar. In the rest/stress patients, one IV will be used for the administration of [⁶⁸Ga]Galmydar and one for the administration of the pharmacological stress agent, regadenoson;
- Collect blood and urine samples for clinical safety lab tests for [⁶⁸Ga]Galmydar participants at screening to be used for a baseline pre-injection measurement and repeated after the imaging prior to discharge post [⁶⁸Ga]Galmydar injection and;
- Perform a brief physical exam for [⁶⁸Ga]Galmydar participants. The screening exam may be used for baseline pre-injection measurement and repeated post [⁶⁸Ga]Galmydar administration;
- Place the participant on the imaging table in supine position with both arms positioned above the head. To ensure participant comfort, place a pillow or folded towels under elbows and pillows or foam wedge under legs of the participant to maintain their position for the duration of the scan;

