10.4 Documenting Adverse Events

All serious and non-serious adverse events as well as abnormal test results/findings, regardless of suspected causal relationship will be documented in the subjects’ research record. Complete appropriate reporting forms according to the guidelines set forth by the Institutional Review Board (IRB) at Washington University Human Research Protection Office (HRPO) and the U.S. Food and Drug Administration (FDA).

Adverse events that are classified as reportable will be followed until resolution or stabilization as evaluated by a physician. Any new relevant clinically significant findings/abnormalities or changes from the subjects’ baseline that meet the definition of an adverse event must also be recorded and documented as an adverse event. All clinically significant changes, relevant medical history and concomitant medications and action taken will be documented in the subjects’ case report forms (source document forms). Events that which do not meet the requirements of SAE reporting will be reviewed and confirmed by the Investigator and reported with the IRB annual continuing review, Data Safety and Monitoring report and the FDA annual report.

The investigator’s clinical determination of any adverse event will be recorded and maintained in the subjects’ research record. All AEs shall be documented on the adverse event log maintained in the regulatory binder.

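### Section 10.3 gives two inconsistent adverse-event rules for pre-existing conditions, which disagree whenever only frequency or only severity increases

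*Combined protocol and SAP*

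**What the plan says.** The second paragraph of Section 10.3 covers conditions already present at consent, which are taken as the participant's baseline. It contains three statements that bear on this point, in this order:

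- **Either-feature rule.** "Worsening of the severity or frequency of a pre-existing condition in a research participant" is called a reportable adverse event, even where the investigational drug is not necessarily the cause.
- **Documentation duty.** "Any changes, i.e., deterioration or worsening in these condition(s) shall be documented and evaluated by the Principal Investigator or designee".
- **Both-features rule.** Adverse events whose signs and symptoms are thought to come from the pre-existing condition "will not be reported as an AE unless there is an increase in frequency and severity".

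Elsewhere, Section 10.2.2 defines an adverse event broadly, as "any untoward medical occurrence in human subjects who receive the investigational radioactive drug", whether or not it is thought to be related. Section 10.4 adds a recording rule: "All serious and non-serious adverse events as well as abnormal test results/findings, regardless of suspected causal relationship will be documented" in the research record. It sends events outside serious-event reporting to the IRB continuing review, the data safety monitoring report and the FDA annual report. Section 7 lists the incidence of adverse events among the measures by which safety is judged.

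**The concern.** The either-feature rule needs one feature to worsen and the both-features rule needs two. The sentences stand in one paragraph with nothing to say which prevails. Two investigators could classify the same event differently and both be following Section 10.3.

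This matters because the incidence of adverse events is a stated safety measure, and Section 1.3 says that human information on the tracer is not yet available. In a study of up to 38 participants, each event carries weight in the safety summary. The question is also a practical one in this population. Section 4.1 states: "Symptomatic patients (n=20) will have undergone a SPECT MPI examination". The exclusion criteria in Section 4.2.2.2 name worsening angina pectoris as an intervening event, so the protocol itself foresees that a baseline condition may worsen.

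**Working it through.** No arithmetic applies. The check sets the two rules side by side over every combination of the two features, for signs and symptoms that the investigator attributes to a pre-existing condition.

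| Frequency increased | Severity increased | Either-feature rule | Both-features rule | Agree? |
|---|---|---|---|---|
| No | No | Not an adverse event | Not an adverse event | Yes |
| Yes | No | Reportable | Not reported as one | **No** |
| No | Yes | Reportable | Not reported as one | **No** |
| Yes | Yes | Reportable | Reportable | Yes |

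The rules conflict in 2 of the 4 cases. More frequent but not more severe angina falls in the second row. Angina is an illustration; Section 10.3 names no condition.

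The next step is to see whether other text settles the conflict.

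1. **The sentence between the two rules (Section 10.3).** It requires worsening to be documented and evaluated. It does not say whether the result is an adverse event.
2. **Section 10.2.2.** The broad definition sits closer to the either-feature rule, but the document does not say that it overrides the more specific sentence in Section 10.3.
3. **Section 10.4.** A change from baseline is recorded as an adverse event if it meets the definition of one. For a pre-existing condition, that leads back to Section 10.3.
4. **Section 7.** It names the incidence of adverse events as a measure and gives no counting rule.
5. **Section 7.2.** Its vital-sign limits mark changes as clinically significant, but leave open whether they meet the adverse-event definition.
6. **Section 9.** It contains no rule specific to adverse events.

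None of these sets a precedence. The conflict remains, and its direction is known: in the two discordant cases the both-features rule gives the lower count.

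**The case against.** The strongest reply is that this is loose drafting with little effect. The either-feature rule says affirmatively that such worsening is reportable, and the general definition supports it. The both-features sentence might be meant only for unchanged background symptoms. Worsening would in any case be seen: Section 10.3 requires it to be documented, Section 6.4.2 has symptomatic patients rechecked before the ammonia scan, and Section 7.4 provides a follow-up call.

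Part of this stands. The event would probably be seen and recorded, so the gap concerns its label and whether it is counted. The background-symptom reading does not work, because the sentence sets its own threshold for when such symptoms become reportable and so governs worsening.

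Three stronger readings are tempting, and the documents do not support them.

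- **A large share of events is lost.** A reader might take the 20 symptomatic participants among the 30 in the rest/stress group as the exposed fraction, or guess how often both features worsen together. The documents give no rate of worsening. They do not say that all 20 have angina, and ten of them have a normal SPECT study. The rule also covers any pre-existing condition in any participant.
- **Harm from stopping vasoactive drugs goes uncounted.** Section 6.2.1 says that calcium-channel blockers, ACE inhibitors, beta-blockers and "nitrates should be discontinued at least 24 hours before the PET perfusion examination". A reader might infer that the resulting symptoms escape. However, adverse-event monitoring runs from injection (note c to Tables 2 and 3), so symptoms before the first injection fall outside the window under either rule. An event attributed to a study procedure, which Section 10.3 allows for, is not covered by the both-features sentence. The number taking these drugs is not given. Only withdrawal before a later visit, with symptoms attributed to the baseline disease, would fit.
- **Hypertension is a second example.** Section 7.2 has its own blood-pressure limits, and frequency hardly applies to a blood-pressure reading.

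**Conclusion.** The inconsistency is real and is in current text. The two rules give different answers when exactly one of frequency and severity increases, and no other section resolves this. In those cases an event that must be documented may or may not be classified, counted and reported as an adverse event. The incidence in Section 7, the adverse-event log and the annual summaries under Sections 10.4 and 12 then rest on the investigator's choice of sentence.

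The size is 2 of the 4 possible cases; the number of events cannot be derived from the documents. A reader might infer that these events are certain to go unreported. That goes too far, since the either-feature rule taken alone requires them to be reported. The defect is inconsistent ascertainment. The conclusion assumes that both sentences are read literally and that both apply to symptoms attributed to a baseline condition. It is not fatal to the trial, but it should be corrected before events are classified.

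**What to change.** In the last sentence of the pre-existing-conditions paragraph in Section 10.3, replace *and* with *or*, so that an increase in either frequency or severity makes the event reportable. This matches the rule stated earlier in the paragraph and fits the broad definition in Section 10.2.2. State that this one rule governs the adverse-event log, the incidence in Section 7, and the IRB, data safety monitoring and FDA summaries. If any events have already been classified, re-check those attributed to pre-existing conditions against it.

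The cost is one word in an amendment and possibly a few more logged events. No dose, procedure or treatment decision changes.

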10.3.1 Severity/Intensity

An adverse event will be classified as one of the following to describe the severity (intensity) and any necessary action taken in an attempt to resolve the event:

- **Mild:** A mild AE is usually transient in nature and generally not interfering with normal activities. Participants are asymptomatic or have mild symptoms; intervention is not indicated.
- **Moderate:** A moderate AE is sufficiently discomforting to interfere with normal daily activities. Participants may need minimal, local, or noninvasive intervention;

- **Severe:** Also referred to as medically significant but not immediately life-threatening; hospitalization or prolongation of hospitalization is indicated; disabling; limiting self-care activities of daily living (ADL). Note that a severe event is not necessarily a serious event.

10.3.2 Attribution

The degree of certainty about causality will be graded using the following relationship categories:

- **Unrelated:** An adverse event is clearly not related to the drug or procedure.
- **Unlikely Related:** An adverse event is doubtfully related to the drug procedure.
- **Possibly Related:** An adverse event is may be related to the drug or procedure.
- **Probably Related:** An adverse event is likely related to the drug or procedure.
- **Definitely Related:** An adverse event is clearly related to the drug or procedure.

For the purposes of regulatory reporting, a causality assessment of unlikely related will be managed as “unrelated.” An adverse event that is definitely, probably, or possibly related will be managed as “related” and considered a “reasonable possibility” that the drug caused the adverse event and, therefore, meets the criteria for reporting to the FDA.

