11.6 Intravenous Catheter Placement

Participants may experience pain, bruising, and/or bleeding at the site of needle insertion for the intravenous (IV) catheter. There is a rare risk of infection from the needle insertion.

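### Section 10.3.2 grades relatedness to drug and procedure as one question, then reads every related grade as pointing to the drug, so procedure-only events are labelled suspected Galmydar reactions

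*Combined protocol and SAP*

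**What the plan says.** Section 10.3 asks the investigator for one determination, the "likelihood that an AE is related to the administration of the radioactive drug or research visit procedure". Its next sentence lists alternative causes to be weighed: "Other etiologies such as pre-existing conditions, concomitant therapy, study-related procedures", among others.

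Section 10.3.2 supplies the scale. Definitely related means "An adverse event is clearly related to the drug or procedure". Possibly related, the lowest grade handled as related, reads "An adverse event is may be related to the drug or procedure". The unrelated and probable grades use the same pairing. The unlikely grade drops the conjunction, apparently by a slip.

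The closing paragraph of 10.3.2 applies to regulatory reporting. Unrelated and unlikely are handled together as unrelated. Possible, probable and definite are handled as related and are taken to give a reasonable possibility "that the drug caused the adverse event and, therefore, meets the criteria for reporting to the FDA". The procedure no longer appears in this sentence.

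Section 10.2.3 says what reasonable possibility means: "evidence to suggest a causal relationship between the drug and the adverse event". An event that meets this test is a suspected adverse reaction. Section 10.2.1 names the drug as Galmydar.

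**The concern.** The scale asks about two causes and the mapping rule answers for one. Nothing between them removes events that the investigator attributes wholly to a procedure. The resulting label, suspected adverse reaction, is the one that the FDA column of Table 1 uses to decide what is reported and how fast.

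The protocol says that no human data on this tracer exist yet, and safety is part of the secondary objective (Section 2.2). What is recorded as suspected of the tracer here will be the first human information of that kind. The same protocol lists risks that belong to the catheter (11.6), the scanner (11.5) and regadenoson (11.4), so procedure-related events are foreseen.

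**Working it through.** No formula or planned figure is involved. The check follows an event through the text.

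**Trace of a catheter-site bruise**

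1. Section 11.6 foresees it: "Participants may experience pain, bruising, and/or bleeding at the site of needle insertion".
2. The investigator is sure that the catheter caused it. Under 10.3.2 the matching grade is definitely related, because the grade is met by either the drug or the procedure.
3. The closing paragraph of 10.3.2 handles that grade as related and as a reasonable possibility of causation by the drug.
4. Under 10.2.3 such an event is a suspected adverse reaction, and under 10.2.1 the drug is Galmydar.
5. Yet 10.2.3 itself asks for evidence against the drug, and in this case there is none. Steps 3 and 4 therefore conflict with the definition that they invoke.

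**Does Section 10.3 repair this?** No. Its first sentence makes the visit procedure part of what is graded, and its second makes study procedures an alternative explanation. Two investigators who both follow the text could grade the same bruise definitely related (first sentence) or unrelated (second sentence).

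**What changes in practice.** Sections 10.5.1 and 10.5.2 expedite an event only if it is also serious and unexpected. Section 10.4 sends other events to the annual reports.

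| Event, caused only by a procedure | Literal 10.3.2 | Drug-only test of 10.2.3 | Difference |
|---|---|---|---|
| Catheter bruise, non-serious | Suspected reaction; annual summary | Not suspected; annual summary | Label |
| Faintness in scanner, non-serious | Suspected reaction; annual summary | Not suspected; annual summary | Label |
| Serious and unexpected | Suspected reaction; 7- or 15-day report | Not suspected; no expedited report as a drug reaction | Label and route |

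**Regadenoson.** It is a drug, but not the investigational drug. The protocol does not say whether its effects are graded as procedure or weighed as concomitant therapy. If as procedure, they follow the same path as the bruise. Flushing, headache and dizziness are listed both for the tracer (11.1) and for regadenoson (11.4), and Section 6.4.1.2 gives the tracer 30 seconds after regadenoson.

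**Who is exposed.** The plan has 8 dosimetry and 30 rest/stress participants, 8 + 30 = 38. All 38 are to have IV access and scans. Regadenoson stress is scheduled for 30 / 38 = 79%. These are counts of people exposed, not of events.

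**Is there a separate attribution elsewhere?** Sections 10.3, 10.4 and 13.1 and the two schedules of activities describe none for Galmydar, regadenoson, ¹³N-ammonia or procedures.

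**The case against.** The best reply is that this is loose wording with little consequence. Section 10.2.3 is specific to the drug, so a sensible reader would apply the mapping to the drug only. A procedure can also properly be one target of relatedness and, when the drug is being judged, a competing cause. That reading is possible, but the protocol does not state it, and the literal rule says otherwise.

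Other parts of the reply stand, and they rule out stronger conclusions that a reader might draw:

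- *That a headline count of drug-related events is inflated.* No such count is defined. Section 7 assesses the incidence of adverse events without a relatedness filter, Section 9 has no safety analysis by relatedness, and the Section 12 report summarises all adverse events. The mapping is itself confined to regulatory reporting.
- *That ordinary catheter, scanner or stress complaints would be expedited to the FDA.* They would not, because non-serious events fail the seriousness test.
- *That the number of mislabelled events can be predicted.* The documents give no rate for any procedure event.
- *That the causes could never be separated later.* The adverse event form is not among the documents, and Section 10.4 requires the investigator's determination to be kept in the research record.
- *That these events become adverse reactions.* Section 10.2.4 reserves that term for events caused by the drug. The label here is only suspected.

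It is also fair to say that separate grades will not settle every case of flushing or dizziness after two injections 30 seconds apart. They would at least record which agent the investigator suspected.

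**Conclusion.** The inconsistency is real and should be corrected. As written, 10.3.2 turns relation to drug or procedure into suspicion of the drug. That contradicts 10.2.3, and 10.3 leaves it unresolved. There are two effects: suspected Galmydar reactions mislabelled in any summary by relatedness, and a serious, unexpected, procedure-only event expedited to the FDA as a suspected drug reaction. The second error is towards over-reporting.

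The conclusion rests on a literal reading of 10.3.2. For regadenoson it also rests on the assumption that the stress test is graded as a procedure. It depends on no assumed event rate, and no count of affected events is claimed.

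**What to change.** - In 10.3.2 and on the adverse event log, record relatedness to Galmydar separately from relatedness to study procedures and to other administered agents (at least regadenoson), each on the existing five-level scale.
- State that only the Galmydar grade triggers the reasonable-possibility and suspected-adverse-reaction mapping.
- Reconcile the first two sentences of 10.3, so that procedures are graded in their own right and count as an alternative cause only when Galmydar is being judged.
- Leave the broader IRB test in 10.6.1.1, relation to taking part in the research, as it is. Procedure-related problems then still reach the IRB.

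The cost is a column or two on the log and a few sentences of text. No visit, test or procedure is added.
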